10.3. Severity

Adverse events will be classified according to one of three levels of severity. The Investigators will use the following definitions to assess the severity of the adverse event:

Mild: The event does not result in limitation of usual daily activities and/or does not require therapy or only symptomatic therapy is required to treat the injury or illness.

Moderate: The event results in some limitation of usual daily activities and/or requires specific therapy to treat the injury or illness.

Severe: The event interrupts the subject's usual daily activities, requires specific therapy and/or is incapacitating leading to hospitalization, emergency treatment, life threatening events, or death.

10.4. Anticipated Adverse Events and Adverse Device Effects

Risks associated with the study devices and the related procedure are based on the current state of the art and an objective review of published data.

10.4.1. Anticipated Adverse Events

The following adverse events may occur and are typically associated with the TIPS procedure:

² If an investigational device gives an incorrect diagnosis, the patient might, for example, receive an unnecessary treatment and incur all the risks that accompany that treatment, or might be incorrectly diagnosed with a serious disease. In other cases, the patient might not receive an effective treatment (thereby missing out on the benefits that treatment would confer) or might not be diagnosed with the correct disease or condition.

Hepatic encephalopathy
Infection/Sepsis
Liver failure
Contrast induced nephropathy
Allergic reaction to contrast utilized intra-procedurally
Adverse reactions associated with administration of general anesthesia or conscious sedation
Death

10.4.2. Anticipated Adverse Device Effects

Adverse events related to the use of the Scorpion set or Cook Transjugular Liver Access set may include the following:

Intraperitoneal hemorrhage or hemoperitoneum
Puncture site hematoma
Cardiac arrhythmia
Cardiac tamponade
Arteriovenous fistula or other arterial injury
Arterio-biliary fistula or biliary tract injury
Extrahepatic Organ Injury
Capsular Perforation
Needle/catheter/guidewire fracture
Foreign body retention

10.5. Reporting Requirements

10.5.1. Site AE Reporting Requirements

Adverse event reporting will start at the time of the TIPS procedure (on Day 0). Adverse events that occur between the signing of the informed consent form and the initiation of the TIPS procedure will not be reported on the eCRF. Underlying diseases are not reported as adverse events unless the condition worsens or re-appears. Adverse event information, including but not limited to the occurrence date, the reported date, procedures, and medications must be recorded in the subject's medical record and reported as part of the study adverse event report. Adverse event information will be collected for all subjects and assessed at every encounter with the subject.

The AE information submitted on the eCRF should include where possible:

Severity of the event
Causality of the event (in relation to the device and/or procedure)
Seriousness of the event
Outcome of the event

Adverse events should be reported by the site on the appropriate eCRF in the EDC system in a timely fashion from discovery by the site.

Serious Adverse Events and Adverse Device Effects must be reported to the Sponsor or designee within 5 working days by the Principal Investigator or designated study staff of discovery.

It is also the responsibility of the Principal Investigator or designee to inform the IRB of adverse events as required per the IRB policies and procedures and, because the study devices are commercially available, Principal Investigators must comply with any institutional user reporting requirements.

10.5.2. Reporting Device Deficiencies

All device deficiencies related to the identity, quality, durability, reliability, safety, or performance of the investigational device shall be documented throughout the clinical study and appropriately managed by the Sponsor. Device deficiencies should be reported by the site by recording them in the EDC within 5 working days of discovery by the site.

It is also the responsibility of the Principal Investigator or designee to inform the IRB of deficiencies, failures, and malfunctions as required per the IRB policies and procedures.

Investigational devices involved in deficiencies, failures, or malfunctions should be retained for return to Argon, where possible. Following the deficiency, failure or malfunction report to Argon, product return information will be provided.

11. STATISTICAL CONSIDERATIONS

11.1. Statistical Design and Methodology

For this post approval study, no formal study hypothesis will be tested. Study outcomes will be presented using descriptive statistics for each treatment group. In addition, outcomes by demographic and clinical characteristics will be presented. For exploratory purposes, between-group differences in study endpoints will be assessed with comparative tests. Statistical analyses will be performed using SAS (SAS Institute, Cary, NC, USA).

11.1.1. Descriptive Results

Unless otherwise specified, for continuous variables, descriptive statistics will include the number of subjects/procedures (N), mean, standard deviation, median, minimum, and maximum values. Categorical variables will be summarized using frequency and percentages.

11.1.2. Exploratory Comparisons

Between-group comparisons will be conducted using Student's t-test for continuous variables and Pearson's Chi-square test for categorical variables. Comparability analysis between two study groups will be first conducted based on demographic and clinical parameters.

Appropriate statistical methods will be employed to explore the correlation and impact of the unbalanced baseline variable, if any, on the study results. When necessary, advanced statistical method such as mixed linear models will be employed to justify the impact.

When sample size permits, the outcomes will be reported for sub-groups such as by gender, age group (≤ 50 years vs > 50 years), type of image used, or operation experience.

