3. INTRODUCTION

Argon Medical Devices Inc. ("Argon") has developed the Scorpion® Portal Vein Access Set ("Scorpion set") to create a pathway through the liver parenchyma through which an endoprosthesis can be delivered. The objective of this post-market clinical study is to evaluate the safety and effectiveness of Scorpion compared to Cook Transjugular Liver Access Set during transjugular intrahepatic portosystemic shunt procedures. This is a post approval study being conducted in the US and will be used to support initial CE mark approval in the EU.

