6.2. Study Hypothesis

No formal study hypothesis will be tested, but it is expected that the safety and effectiveness of the Scorpion set are similar to the Cook Transjugular Liver Access Set.

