6.4.3. Secondary and Exploratory Endpoints

The secondary and exploratory endpoints of this clinical study are outlined in **Table 5**.

TABLE 5. OVERVIEW OF SECONDARY AND EXPLORATORY ENDPOINTS

Endpoint	Description / Definition
Secondary Endpoints	
Portal Vein Access (PVA) time	Time (in minutes) from initial needle throw to portal vein access as confirmed by portogram
Technical success	Creation of a shunt (stent bridging) between the portal and systemic veins
Number of needle passes	Count of needle throws between the hepatic and portal vein to create the parenchymal tract
Procedure duration	Interval (in minutes) from first jugular access for TIPS creation to removal of catheters from subject
Fluoroscopy time	Measured in minutes
Device-related complications	Incidence of complications related to the device as judged by the Principal Investigator
Exploratory Endpoints	

Change in MELD score	Change in score from Screening to Day 30
Change in Child-Pugh score	
Radiation dosage	Measured in air kerma (mGy)
Contrast volume used	Measured in mL
Length of Hospital Stay	Measured in days
Number of ICU days	Measured in days
Change in HPVG	Measured in mm Hg

MELD = Model for End-Stage Liver Disease; ICU = Intensive Care Unit; HPVG = Hepatic Venous Pressure

Gradient

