11.6. Statistical Deviations

Any *post hoc* or unplanned analyses not identified in this protocol will be clearly identified in the Clinical Study Report.

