13.10. Minimization of Bias

The following activities are intended to reduce the risk of bias:

- Randomized study
- Objective methodology to evaluate endpoints
- Stratified randomization (if applicable after the interim analysis)

Furthermore, potential for bias has been minimized with a well-controlled design, expected conduct under the terms of the approved protocol, use of specific inclusion and exclusion criteria, careful definitions for study procedures and outcomes, and prospectively defined methods of data analysis.

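### No confidence interval is planned for procedural success, major complications or their between-group difference; at 30 per arm this is an inexpensive precision improvement, not an error

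*Combined protocol and SAP*

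**What the plan says.** Section 11.1 tests no formal hypothesis and presents outcomes descriptively by arm. It then adds: "For exploratory purposes, between-group differences in study endpoints will be assessed with comparative tests". For binary outcomes, Section 11.1.1 says "Categorical variables will be summarized using frequency and percentages". The comparative method, in Section 11.1.2, is: "Between-group comparisons will be conducted using Student's t-test for continuous variables and Pearson's Chi-square test for categorical variables". The synopsis and Sections 11.1 to 11.7 contain no confidence interval and no precision target, and no separate SAP is mentioned that might add them.

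Three other places give context. Section 6.2 states no hypothesis but says "it is expected that the safety and effectiveness of the Scorpion set are similar to the Cook Transjugular Liver Access Set". Section 3 says the study "will be used to support initial CE mark approval in the EU". Section 11.2 calls the sample size empirical, and Section 6.6 sets it at about 30 per group.

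For the exploratory MELD and Child-Pugh endpoints, Table 5 (Section 6.4.3) gives "Change in score from Screening to Day 30". Section 11.1.2 would compare these changes by t-test. It provides for baseline adjustment only where a baseline variable is unbalanced or where it is judged necessary.

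**The concern.** With no hypothesis and no margin, the main product of the comparison is the size of the difference and its uncertainty. The size can be read from the reported percentages. The uncertainty is not planned for, on either primary endpoint.

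A reader can build an interval from the counts, but must first choose a method, and in small samples with rates near 0% or 100% that choice can change the impression. The planned test also returns nothing if every procedure succeeds, or if no major complication occurs, in both arms.

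A smaller matter is that the t-test on change in MELD or Child-Pugh leaves unused a baseline value that the study already collects.

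**Working it through.** **Inputs.** n=30 per arm (Section 6.6). The documents give no significance level, margin or expected rate for either primary endpoint, so two-sided 5% and 95% are assumptions. The nearest rates, both in Section 3.2, are for different endpoints: 100% technical success in 15 retrospective Scorpion X cases, and 3.6% puncture-related complications with the Cook sets. The plan has no precision figure to reproduce. Differences below are first arm minus second.

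**1. Success 25/30 versus 29/30.**
- Pearson: pooled rate 54/60=0.90. Statistic = (0.1333)²/(0.90×0.10×2/30) = 0.01778/0.006 = 2.96, p=0.085.
- Wilson limits per arm: 0.664 to 0.927 and 0.833 to 0.994.
- Newcombe lower limit: -0.1333 - √[(0.8333-0.6644)² + (0.9941-0.9667)²] = -0.1333 - 0.171 = -0.305.
- Newcombe upper limit: -0.1333 + √[(0.9266-0.8333)² + (0.9667-0.8333)²] = -0.1333 + 0.163 = +0.029.
- Miettinen-Nurminen: -31.0 to +2.5 points.

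**2. Complications 4/30 versus 1/30.** Pearson p=0.16; Newcombe -5.6 to +26.6 points; Miettinen-Nurminen -5.3 to +27.1.

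**3. Identical results, 30/30 versus 30/30.**
- Pearson: the pooled variance is zero, so the statistic is undefined.
- Wald: zero width.
- Newcombe: the limits are ±z²/(n+z²) = 3.8415/33.8415 = 0.1135, or ±11.4 points.
- Miettinen-Nurminen: its variance factor is 60/59, so z² becomes 3.8415×60/59 = 3.907 and the limits are ±3.907/33.907 = ±11.5 points.

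The same holds at 0/30 versus 0/30. If the true rate were 3.6% in both arms, that table would occur with probability 0.964^60 = 11%.

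**4. Single arm, Clopper-Pearson.** 30/30 gives 88.4% to 100%; 29/30 gives 82.8% to 99.9%; 0/30 gives an upper limit of 11.6%.

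**5. Does the method matter?** At 26/30 versus 30/30, Pearson p=0.038.

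| Method | 95% interval (points) |
|---|---|
| Wald | -25.5 to -1.2 |
| Newcombe | -29.7 to +0.6 |
| Miettinen-Nurminen | -29.8 to -1.0 |

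Of the 31×31=961 possible tables, Pearson is defined in 959. Newcombe contradicts it at the 5% level in 8: 26 v 30, 24 v 29, 0 v 4, 1 v 6, and the same four with the arms exchanged. All 8 have one arm within one event of 0% or 100%, the region where the Section 3.2 proxies sit.

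At zero difference the Miettinen-Nurminen statistic is Pearson's multiplied by 59/60. The two could disagree only if Pearson's statistic fell between 3.841 and 3.907, and no table at 30 per arm gives such a value.

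**6. ANCOVA against change score.** With pre/post correlation rho and post/pre SD ratio k, both assumed, the variance ratio is k²(1-rho²)/(1+k²-2·rho·k). At k=1 this is (1+rho)/2.
- k=1, rho 0.3, 0.5, 0.8: variance lower by 35%, 25%, 10%. Allowing for the extra degree of freedom (factor about 1+1/56=1.018), about 34%, 24%, 8%.
- rho 0.5, k=0.8: ratio 0.571, lower by 43%.
- rho 0.5, k=1.25: ratio 0.893, lower by 11%.
- rho 0.8, k=1.25: ratio 0.5625/0.5625 = 1, no gain.

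**The case against.** The study says it is descriptive, its comparison is labelled exploratory, and its sample size is declared empirical. The report would show 25/30 (83.3%) and 29/30 (96.7%) beside the p-value, so the size of the difference is not hidden. The tests are valid, and any reader can compute an interval. All of this stands, and it limits the point to a reporting improvement.

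Several stronger readings are tempting but unsupported:
- **That the plan will treat a non-significant p-value as similarity.** Section 6.2 states an expectation. No section draws that conclusion from a test.
- **That an interval added at reporting would break the plan.** Section 11.6 says only that "unplanned analyses not identified in this protocol will be clearly identified in the Clinical Study Report", so a later interval would need a label. Section 13.10 does cite "careful definitions for study procedures and outcomes, and prospectively defined methods of data analysis" as a guard against bias, but in general terms. What remains is that a method chosen after seeing the data leaves discretion, and step 5 shows that this can matter.
- **That the CE mark purpose demands a given precision.** No section links that use to a between-group inference or an interval width.
- **That the interval would settle similarity.** It cannot without a margin, and the documents give none.

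On ANCOVA, the objection is that the gain rests entirely on assumed values. Equal variances are doubtful for MELD, because Section 7.3 excludes screening scores of 18 or more while Day 30 scores are not capped. Section 11.1.2 also already allows some adjustment. This is fair, and is why that part is secondary.

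**Conclusion.** The gap is real and modest. Neither primary endpoint has a planned interval, per arm or for the difference. At 30 per arm the missing information is substantial: identical perfect results leave about ±11 points of uncertainty, and a p-value of 0.085 can accompany an interval from about 30 points worse to 3 points better. These figures assume 30 analysed subjects per arm and two-sided 95% intervals; the example counts are illustrations, not forecasts. It should not be read as an invalid analysis or as a claim of similarity that the protocol does not make.

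The ANCOVA suggestion concerns exploratory endpoints only. Its gain lies between nil and 43% lower variance over the scenarios shown.

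**What to change.** In Section 11.1, for procedural success and major complications:
- Prespecify a two-sided Clopper-Pearson 95% interval for each arm.
- Prespecify a Miettinen-Nurminen score 95% interval for the difference. It is preferred to Newcombe because it agrees with the retained Pearson test.
- Report both beside the counts and the exploratory p-value, and state that a non-significant p-value will not be described as similarity.

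Secondary, exploratory endpoints only: analyse Day 30 MELD and Child-Pugh by ANCOVA adjusted for the screening value, in place of the t-test on change. Do the same for the pressure gradient, with the pre-stent reading as covariate, only if the pre- and post-stent measurements in Section 8.3 are confirmed as the change meant in Table 5, which gives no time points for it.

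Cost: a few sentences and standard SAS output, with no new data and no change to conduct or sample size. The downsides are that wide intervals become visible and that ANCOVA uses one degree of freedom, possibly for no gain.

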Secondary Endpoints	
 Portal vein access (PVA) time defined as the time between initial needle throw to portal vein access confirmed by portogram Technical success defined as creation of a shunt (stent bridging) between the portal and systemic veins Number of needle passes Procedure duration defined as the interval from the first jugular access for TIPS creation to removal of catheters from the subject Fluoroscopy Time Device-Related Complications, in the judgment of the Principal Investigator
Exploratory Endpoints	
 Change in Model for End-Stage Liver Disease (MELD)/Child-Pugh score Radiation dosage measured in Air kerma (mGy) Contrast volume used Length of hospital stay and number of ICU days Change in hepatic venous pressure gradient (HPVG)
Arms and Interventions	
Two Arms:
 
 Procedure with the Scorpion Portal Vein Access Kit Procedure with the Cook Transjugular Liver Access Set 
Intervention:
 
Subjects will undergo a transjugular intrahepatic portosystemic shunt procedure during which portal vein access will be obtained using the Scorpion (Group 1) or Cook (Group 2) device.

Follow-up Visits	
Subjects will be evaluated at:
 
 Screening TIPS Procedure Discharge Day 7 post-procedure Day 30 post-procedure 
Evaluation includes the following procedures/assessments:
 
 - Medical history - Physical examination - Laboratory values (e.g., complete blood count, comprehensive metabolic panel, prothrombin time, and international normalized ratio) - MELD score - Child-Pugh Score - TIPS Procedure information - Imaging (i.e., ultrasound, computed tomography or magnetic resonance imaging, and echocardiogram) - Adverse events assessment

Clinical Investigation Plan (CIP)

CP-2023-001: Achieving Portal Access with Scorpion Post-Approval Study

Revision: C

Argon Location: All Sites

Total Duration	Estimated enrollment period: Approximately 6 months Study duration for the subject: Approximately 1 month Total study duration: Approximately 7 months
Clinical Study Population	
Population	The study population will consist of subjects undergoing a TIPS procedure for refractory variceal bleeding, refractory ascites and/or hydrothorax. The planned sample size is 60 subjects (30 per group). The planned sample size is empirical, as no formal statistical hypothesis will be tested.

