7.7. Randomization

Randomization will occur after an eligible subject has signed the ICF and prior to initiation of the TIPS procedure. Subjects will be randomly assigned at a 1:1 ratio into one of the two study groups (Scorpion or Cook) via a centralized randomization service.

Once the randomization assignment is received, the physician will determine the model he/she wants to use based on preference, training, and the subject case before beginning the procedure.

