11.3.3. Safety Population

Safety set will include all procedures/patients defined in the intent-to-treat set.

This set will be the base for the overall study safety assessment.

For study device-specific post-operation safety assessment, only those included in the primary effectiveness set will be used.

Comparability analyses between the two study groups will be conducted on the Intent-to-Treat analysis set.

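### Continuous endpoints are compared unadjusted, with baseline covariates considered only if they look unbalanced; this gives up precision that pre-specified adjustment would keep, most simply for MELD and Child-Pugh change

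*Combined protocol and SAP*

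**What the plan says.** Section 11.1.2 of the combined protocol and SAP sets the default: "Between-group comparisons will be conducted using Student's t-test for continuous variables and Pearson's Chi-square test for categorical variables". It then adds a baseline step: "Comparability analysis between two study groups will be first conducted based on demographic and clinical parameters". Section 11.3.3 places that step on a particular set: "Comparability analyses between the two study groups will be conducted on the Intent-to-Treat analysis set".

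Covariates enter only after this. Unspecified methods will "explore the correlation and impact of the unbalanced baseline variable, if any, on the study results", and the section continues: "When necessary, advanced statistical method such as mixed linear models will be employed to justify the impact". There is no list of covariates, no definition of imbalance, no threshold and no adjusted model.

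Two candidate covariates are visible elsewhere in the plan:

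- Table 5 in Section 6.4.3 defines the MELD and Child-Pugh endpoints as "Change in score from Screening to Day 30", so the screening score is to hand.
- Section 3.2 cites mean portal access times of 46 minutes with conventional fluoroscopy and 31 minutes with intravascular ultrasound. Section 11.5 may make imaging technique a stratification factor after the interim look.

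Section 7.7 randomises 1:1 without initial strata, and the synopsis plans 30 subjects per group. All comparisons are labelled exploratory (Sections 11.1 and 11.2).

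**The concern.** After randomisation, a difference between arms in a baseline variable is mostly the luck of the draw. It carries no information on whether the variable predicts the outcome. A rule that looks only at imbalance will usually pass over a strongly prognostic variable that happens to be balanced, and will sometimes pick up an irrelevant one that is not.

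What is at stake is precision. With 60 subjects and no hypothesis test, estimates and their intervals are the main product of the study, and Sections 3 and 3.3 say the data will support an initial CE mark application. Section 13.10 also lists prospectively defined analysis methods among the safeguards against bias. For covariate adjustment, Section 11.1.2 does not supply them.

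**Working it through.** The documents give no figure on baseline testing or adjustment to reproduce. The sample size is simply 2 × 30 = 60. Everything marked *assumed* below is not in the documents.

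**1. Chance flags.** *Assumed:* 10 independent baseline tests at two-sided 5%. The chance of at least one flag is 1 − 0.95^10 = 0.401. With 5 tests it is 0.226 and with 20 it is 0.642. A given prognostic variable is flagged in only about 5% of trials.

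**2. Where the precision goes.** Simulated trials with 30 per arm, a continuous outcome with SD 1, one covariate, and an *assumed* 5% trigger whose adjusted result replaces the t-test. Standard error of the treatment difference:

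| Assumed correlation | Unadjusted | Adjust only if flagged | Always adjust |
|---|---|---|---|
| 0.5 | 0.257 | 0.248 | 0.226 |
| 0.7 | 0.257 | 0.240 | 0.185 |

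At 0.5, always adjusting saves 0.257 − 0.226 = 0.031, while adjusting on a flag saves 0.257 − 0.248 = 0.009. The loss comes from not adjusting by default; the baseline test is not itself the cause. The correlations of 0.5 and 0.7 are illustrations with no source in the documents.

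With ten variables screened, one of them prognostic, mean 95% interval widths were:

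| Assumed R² | Always adjust | Adjust on flag | Ratio |
|---|---|---|---|
| 0.02 | 1.028 | 1.054 | 1.025 |
| 0.10 | 0.986 | 1.053 | 1.068 |
| 0.25 | 0.901 | 1.049 | 1.16 |

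The unadjusted width was about 1.03 throughout. Test size for adjust-on-flag was 0.047 at R² = 0.10 and 0.044 at 0.25, which is slightly conservative.

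**3. MELD and Child-Pugh change.** Let r be the correlation between screening and Day 30, and k the ratio of the screening SD to the Day 30 SD. In units of the Day 30 variance:

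- change score: 1 + k² − 2rk
- ANCOVA on the screening score: 1 − r²
- difference: (k − r)², which is never negative

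With k = 1 (*assumed*) the variance ratio is (1 − r²)/(2(1 − r)) = (1 + r)/2.

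- r = 0.5: ratio 0.75, and √0.75 = 0.866, so the interval is about 13% narrower.
- r = 0.8: ratio 0.90, and √0.90 = 0.949, so about 5% narrower.

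Estimating the slope costs a factor of about 57/56 = 1.018 in variance, which takes a little under one percentage point off each gain. If k falls to r the gain vanishes. Excluding MELD of 18 or more at screening could push k below 1.

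**4. Imaging and access time.** Difference 46 − 31 = 15 minutes (Section 3.2). *Assumed:* a 50/50 imaging split and a within-technique SD of 15 to 30 minutes. Between-technique variance is 15²/4 = 56.25.

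- SD 15: R² = 56.25/(56.25 + 225) = 0.20
- SD 30: R² = 56.25/(56.25 + 900) = 0.06

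Compared with always adjusting, adjusting only on a 5% flag costs about 3% to 18% in variance by simulation. Never adjusting, which is the default t-test, costs (1/(1 − R²)) × 56/57 − 1, or about 4% to 23%.

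**5. Binary endpoints.** At the 3.6% puncture-complication rate in Section 3.2, used only as an illustration, 60 × 0.036 = 2.2 events are expected. That is too few for a covariate model.

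**The case against.** The best defence is that Section 11.1.2 does not state the rule simulated above. It gives no 5% trigger and never says that an adjusted result replaces the t-test. The covariate paragraph can be read as a follow-up sensitivity look. That stands, and it is why the point rests on the unadjusted default, with baseline testing secondary.

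Three further objections stand in part.

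- Everything is exploratory, so no confirmatory error rate is at risk. This limits the importance, although precision still matters in a study that exists to estimate.
- The intent-to-treat set is confined to attempted procedures in an open-label trial (Sections 7.8 and 11.3.1), so losses before the procedure could add imbalance that is not chance. That is a reason to describe baseline carefully, but it does not make imbalance a guide to prognosis.
- Imaging is already a reporting subgroup and a possible stratification factor. Neither puts it in the comparison model.

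A reader might infer that the plan raises the false-positive rate, or lets the sponsor choose a favourable model. The documents support neither. Under a fixed rule the test is slightly conservative, and Section 11.6 commits to identifying unplanned analyses in the report. The wording leaves discretion, but nothing shows it will be used selectively. A reader might also extend the precision gain to procedural success or major complications. Those are binary. Success was 100% in the 15 earlier cases that Section 3.2 cites, and in simulation with a strong covariate, adjustment raised the standard error of the log odds ratio from 0.57 to 0.69, because it targets a different, conditional quantity.

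**Conclusion.** The point holds for continuous secondary and exploratory endpoints, as a modest loss of precision and of clarity. The firmest part is the score change: ANCOVA on the screening value is never worse than the change score apart from one degree of freedom. It narrows the interval by about 5% to 13% for assumed correlations of 0.8 to 0.5 with equal SDs at the two visits, and by less if the screening scores are less spread.

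For access time, the cited imaging difference implies a cost of about 3% to 18% in variance if imaging enters only when flagged, under the assumed split and SDs. This part is weaker. Section 11.3.2 analyses the time endpoints only in successes with the assigned type of device, a subset formed after randomisation, so the gains of a fully randomised comparison do not transfer cleanly. For weak covariates the gain is near zero.

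**What to change.** In Section 11.1.2:

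1. Present the baseline table descriptively, and do not use it to select covariates.
2. Analyse MELD and Child-Pugh change by ANCOVA with the screening score as covariate, whatever the observed balance.
3. Label any adjustment prompted by observed imbalance as sensitivity analysis.

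These are wording changes. Table 6 already collects both scores at screening and Day 30.

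Optionally, adjust access time, procedure duration and fluoroscopy time for primary imaging technique, in particular if it becomes a stratification factor under Section 11.5. Section 8.3 records only the imaging used, and in an open-label trial that choice can follow knowledge of the assigned device. The covariate should therefore be the planned technique, recorded before randomisation. The cost is one added field, by protocol amendment with IRB approval if required.
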